Seizure Frequency through Diary Data Collection			X	X	X	X
NIH Emotional Measures or Bayley Emotional Scales ^d			X			
Social Determinants of Health data collection			X			
Titrate CBD (if needed)					X	X
Dispense Medication			X		X	X
AE/SAE Monitoring/Reporting				X	X	X

UAB CBD Program: Children's Protocol Schedule of Events (Patients 1 years to 18 years of age) -Page 3 of 5

Activities/Procedures:	SV7/Day 84 (+/- 3 days) or Follow up study visit 28 days after after Target dose is reached:	SV10/Day168/Wk 24/Month 6 (+/- 7 days), SV 14/Day 504/Wk 96/Month 24 (+/- 7 days), SV18/Day 840/Wk 192/Month 48 (+/- 7 days):	SV8/Day 112/Wk 16/Month 4 (+/- 7 days), SV9/Day140/Wk 20/Month 5 (+/- 7 days), SV11/Day 252/Wk 36/ Month 9 (+/- 7 days), SV12/Day 336/Wk 48/ Month 12, SV13/Day420/Wk72/ Month 18, SV15/Day 588/Wk 120/ Month30, SV16/Day 672/Wk 144/Month 36, SV17/Day 756/Wk 168/ Month 42:	Unscheduled Visit or Early Termination Visit (prior to year 1 visit):	Post-Termination Study Visit (approximately 28 days after CBD wean):
Seizure Frequency through Diary Data Collection	X	X	X	X	X
Chalfont Seizure Severity Scale	X	X	X	X	X
Neurological Exam	X	X	X	X	X
General Physical Exam	X	X	X		
Laboratory Assessments ^e	X ^e	X ^e	X ^e	X ^e	X ^e
Electrocardiogram (ECG)				X (at early term visit prior to year 1 only)	X
Urine Pregnancy Test (only for women of child bearing potential)	X	X	X	X	X
Menstrual History Data	X	X	X	X	X
EEG ^a (30-60 minute) duration	X	X ^a	X ^{a,g}	X ^c	
Vital Signs (age, weight, height, HR, BP,	X	X	X	X	X
Pediatric Cognitive Testing (NIH Toolbox), ABAS-II or Bayley Functional Scales ^b		X		X ^c	
Quality of Life in Childhood Epilepsy (QOLCE)		X		X ^c	
Adverse Events Profile	X	X	X	X	X
Columbia Suicide Severity Rating Scale (C-SSRS)	X ^a	X	X	X	X
Child Behavioral Checklist Assessment	X	X			
NIH Emotional Measures or Bayley Emotional		X (SV10 only)	X (SV12 only)		
Social Determinants of Health data collection		X		X ^c	
Titrate CBD (if needed)	X	X	X	X	
Dispense Medication	X	X	X	X (if needed)	
AE/SAE Monitoring/Reporting	X	X	X	X	X

X* =Participants' who have an Enrollment Visit and Study Visit1/Day 0 conducted on the same day will have the following activities performed only once during the visit: Urine Pregnancy test, Seizure Frequency Calendar, Chalfont Seizure Severity Scale, Neurological Exam, General Physical Exam, and Vital signs.

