- Development of anemia with Hemoglobin <10 or Hematocrit <30 or WBC < 2000

If the subject wishes to discontinue the study drug for any reason, the subject will be seen for an early termination visit/end of study visit. The early discontinuation visit will include a CBC, CMP, UA and an ECG.

Study Design

Dosing Adjustment/Schedule:

The titration of CBD will start with a dose of 5 mg/kg/day given in two divided doses and titrated by 5 mg/kg/2 weeks up to 25 mg/kg/day; in some patients additional titration by 5mg/kg/day every 2 weeks upto 50mg/kg/day may be instituted at the discretion of the PI upon discussion with the Co-PI ([name]) Patients will be monitored for adverse events and the dose will be reduced or the titration slowed if there are dose-limiting side-effects.

For any clinically significant ($> 3 \times \text{ULN}$) elevation of ALT or AST, the following laboratory measures, at minimum, should be assessed within 72 hours: repeat ALT/AST, total bilirubin, alkaline phosphatase, and GGT.

- Epidiolex® will be discontinued in patients who have:
 - ALT or AST $>8 \times \text{ULN}$
 - ALT or AST $>5 \times \text{ULN}$ for more than 2 weeks
 - ALT or AST $>3 \times \text{ULN}$ **and** (TBL $>2 \times \text{ULN}$ **or** INR >1.5)
 - ALT or AST $>3 \times \text{ULN}$ with the appearance of fatigue, nausea, vomiting, right upper quadrant pain or tenderness, fever, rash, and/or eosinophilia ($>5\%$)

All trial subjects with elevated LFTs will be followed until all abnormalities return to the baseline state as assessed by the investigator with AST/ALT $< 3 \times \text{ULN}$.

If a subject has elevated LFTs ($>3 \times \text{ULN}$) and is on valproic acid the subject must stop the CBD and the LFTs must be monitored until the return to baseline state. If the subject has shown an improvement in their seizure frequency with the addition of CBD the option to “rechallenge” CBD will be at the discretion of the study PI. It would require that the subject taper off valproic acid and be on a stable dose of antiepileptic medication for 30 days prior to restarting the CBD. They would have repeat baseline labs (CBC, CMP and AED levels) prior to restarting the CBD.

The dose may be maintained at any point in the titration if seizures are controlled (no seizures since last medication adjustment) or there are limiting side effects, or the maximum dose is reached.

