While the dose of 25 mg/kg/day divided into two daily doses will be the standard maximum dose, patients who did not achieve complete seizure control but have exhibited clear improvements in seizure control (e.g., minimum decrease in seizure frequency by 50%) and who have no or minimal side effects of the CBD oil additional increases by 5 mg/kg/day every 2 weeks up to the maximum dose of 50 mg/kg/day may be instituted if both PIs ([name] & [name]) agree that this is in the best interest of the patient. This approach mimics clinical practice as antiepileptic drugs are typically adjusted based on clinical response and presence or absence of side effects.

If a subject experiences a “clinically significant” or “dose limiting” AE or SAE attributable to CBD, the investigator will determine if a dose reduction or taper is necessary. Dose decreases will occur if the patient needs to be tapered off CBD (dose-limiting side effects or lack of tolerability); these decreases will occur in 5 mg/kg/day increments every two week (or at a rate that is felt appropriate by the treating provider).

The CBD cannot be stopped all at once as this could cause the patients seizures/epilepsy to become worse.

The participant may be maintained on a dose lower than maximum amount (50mg/kg/day) if that dose, in the opinion of the patient, LAR, and the study physician, has adequately improved their seizure frequency or severity. The investigator, in consultation with the subject and/or caregiver, will determine when an adequate level of seizure frequency and/or severity of control has been achieved.

Once the subjects reach the dose of 10 mg/kg/day further dose adjustments (upward or downward) can be made biweekly at study visits in order to evaluate safety and establish a target dose up to a maximum dose of 50mg/kg/day in twice daily dosing. Dose adjustments (upward, downward, or taper) may continue until seizure control reached (target dose), maximum dose reached, or dose-limiting side effects are experienced.

Patients referred to the CBD study and approved by the CBD Treatment Approval Committee may have an enrollment visit combined with Study Visit 1 (Day 0), at the discretion of the investigator.

Enrollment Visit Procedures:

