- For participants who are unable, due to cognitive impairment, to complete the Cognitive subtests from the NIH Toolbox, their legal guardian will be asked to complete the Adaptive Behavior Assessment Scale – II (ABAS-II). The ABAS-II measures adaptive behavior, using parent-report to evaluate function across a variety of environments. Test results include four domain composite scores (Conceptual, Social, Practical, and General Adaptive Composite) and 10 skill area scores (Communication, Community Use, Functional Academics, Health and Safety, Home or School Living, Leisure, Self-Care, Self-Direction, Social, and Work/Motor).
 - For participants who are < 3 years of age, Bayley Scales of Infant and Toddler Development®, Third Edition (Bayley-III®)-Functional Assessments will be completed by the parent or LAR of the participant, instead of the NIH Toolbox Cognitive Assessments.
 - Social Determinants of Health (SDH) – Comprehensive SDH information will be collected at the onset. Selected SDH variables may be re-assessed and includes:
 - Biosocial variables (age, date of birth)
 - Socio-demographic variables (education, family structure, family income, financial strain, health insurance status, overall health, health care access/utilization)
 - Psychosocial variables (health literacy, health information sources, social stress, social support, optimism, self-efficacy)
 - Behavioral variables (physical/social activity)
 - Individual-level social relationship domains (exposure to discrimination/violence, self esteem rating, religious participation)

- Geocodable information (address to identify US census tract/block) to link to neighborhood/community-level published national/state socioeconomic and racial/ethnic composition indicators

Post-Termination Study Visit (approximately 28 days after end of CBD study):

Procedures for this visit will include:

- Adverse Event and Serious Adverse Event Monitoring (e.g., increase in seizure frequency by more than 100% leading to emergency room visit or hospitalization)
- Seizure Diary Data reviewed and collected by study staff
- Menstrual History collected by study staff
- Chalfont Seizure Severity Scale
- Vital signs: Age, Weight, Height, Heart Rate, and Blood Pressure, Temperature
- Urine Pregnancy Test (only for women of child bearing potential)
- Neurological Examination
- C-SSRS (Columbia Suicidality Symptom Rating Scale Questionnaire)

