Adverse Events (AEs) for this study are defined as the appearance of (or worsening of any pre-existing) undesirable sign(s), symptom(s), or medical condition (s) that may occur after the patient's signed the informed consent for the study. Abnormal laboratory values or test results occurring after the informed consent is signed constitutes adverse events only if they induce clinical signs or symptoms, are clinically significant, require therapy, or changes in study medication(s).

AEs that begin or worsen after the informed consent should be recorded in the Adverse Event CRF and will be entered in the UAB CBD data coordinating center database. Conditions that are already present at the time of informed consent will be documented as part of the patient's medical history. Subjects and their families will be provided with contact information in order to notify study personnel of any adverse events, with availability at all times. Upon notification of an AE, a determination will be made by study personnel with regard to whether the AE is study related. This determination will be made within 24 hours of receipt of documentation of the AE. If the AE has involved participation of any other medical personnel or facilities, documentation of that activity will be obtained by study personnel for review. The AE will be monitored until it has resolved by the study investigator. AEs will be assessed to determine the following parameters: severity, duration, relationship to the CBD administration, action taken or treatment instituted, and whether the AE meets the criteria for a serious AE. Adverse Events will be assessed according to the Common Terminology Criteria for Adverse Events (CTCAE).

All clinically significant abnormalities noted upon physical examination, or other diagnostic test results should be reported as an AE, except for baseline measurements that may be considered part of the medical history. In addition, all clinically significant AEs that continue at Study Termination should be followed up by the investigator and evaluated with additional tests if necessary, until the underlying cause is diagnosed or resolved, or is determined to have resolved with sequelae. All AEs will be evaluated for

intensity and causal relationship with use of the study medication (or study procedures if applicable) by the investigator.

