AEs that occur following completion of study termination/early termination procedures should be recorded on the AE page of the source documents only if the investigator considers the event as clinically significant and as related to study medication or study procedures.

All adverse events that are deemed to be serious and meet the definitions provided in section below for serious adverse events will be reported as SAEs.

Serious Adverse Events :

Serious adverse event is defined as “ANY TREATMENT EMERGENT SAE THAT OCCURS AFTER THE SIGNING OF THE INFORMED CONSENT FORM through 30 DAYS after administration of the last dose of study medication. Any AE that results in any of the following outcomes will be considered an SAE. The following outcomes are defined according to Code of Federal Regulations (CFR) Title 21 part 312.32.

- Death
- Life-threatening situation (subject was at risk of death at the time of the event. This does not refer to an event that might have caused death if it was of greater intensity.)
- Inpatient hospitalization or prolongation of existing hospitalization
- Persistent or significant disability or incapacity
- Congenital anomaly or birth defect
- Important medical events that may not result in death, be life-threatening, or require hospitalization but may jeopardize the subject and may require medical or surgical intervention to prevent one of the above outcomes (based upon appropriate medical judgment), e.g., allergic bronchospasm requiring intensive treatment in an emergency room or at home, blood dyscrasias or convulsions that do not result in inpatient hospitalization, or the development of drug dependency or drug abuse.

The term “severe” is often used to describe the intensity (severity) of a specific event (as in mild, moderate, or severe pain); the event itself, however, may be of relatively minor medical significance (such as severe headache). By contrast, the term “serious” is used to describe an event based on an event outcome or actions usually associated with events that pose a threat to a patient’s life or functioning. Seriousness (not severity) serves as a guide for defining regulatory reporting obligations.

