DSMB recommendations will be communicated to the principal investigator in writing. The DSMB is expected to make its recommendations based on its best judgment, drawing on its clinical and biostatistical expertise and experience, and taking into account all available sources of information, including other studies if available and the totality of the data reviewed.

In the case of recommendations for early trial termination or modification of trial protocol from the DSMB, the principal investigator and study team will thoughtfully review and consider the DSMB recommendations and will communicate its decisions to the DSMB in writing.

In the event that the Principal Investigator, [name], decides to prematurely terminate the study, it is the Principal Investigator's responsibility to promptly inform sub-investigators and other study staff, relevant regulatory authorities, GW Pharma, and the DSMB.

The principal investigator will be responsible for reporting SAE, AEs and unanticipated problems involving risks to subjects to their local IRBs/ethics committees (ECs) in accordance with local regulations, and any other regulatory agencies that require SAE/AE reporting. All deaths, regardless of presumed causality, unexpected fatal, or life threatening unexpected/suspected adverse reactions will be reported, as required, to the IND and the Division of Neurology Products at the FDA, as IND safety reports.

No special procedures, precautions or follow-up, except for an early termination visit, will occur with currently enrolled participants if the study is stopped. Subjects will be advised to continue treatment with their primary treating neurologist. Subjects will receive standard of care from their primary treatment team regardless.

The study team excludes pregnant women and does testing to minimize the risk of enrolling these women. Further, patients who are women of childbearing potential and male patients with partners of childbearing potential are informed that they should use an effective form of birth control during study participation to avoid any study drug effects on the fetus.

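### The rule for a stopped study allows only an early termination visit, which contradicts the protocol's own follow-up of ongoing AEs, raised liver tests and the post-wean visit

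*Protocol*

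**What the plan says.** The Data Safety Monitoring Board (DSMB) section of the protocol sets out what happens if the study is stopped: "No special procedures, precautions or follow-up, except for an early termination visit, will occur with currently enrolled participants if the study is stopped". Children are then advised to continue with their primary treating neurologist and receive standard care there. The sentence does not limit the reason for the stop. It therefore also covers the safety stop in the same section, which applies when more than 25% of subjects have drug-related SAEs.

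Other protocol sections ask for more:

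- **Adverse Events:** "all clinically significant AEs that continue at Study Termination should be followed up by the investigator and evaluated with additional tests if necessary", until the cause is diagnosed or the event has resolved.
- **Dosing Adjustment/Schedule**, with near-identical text in the section on withdrawal and early termination: "All trial subjects with elevated LFTs will be followed until all abnormalities return to the baseline state".
- **Schedule of Events:** a separate column headed "Post-Termination Study Visit (approximately 28 days after CBD wean". The visit text is headed differently: "Post-Termination Study Visit (approximately 28 days after end of CBD study". The visit includes AE review, seizure diary, Chalfont scale, neurological examination, suicidality scale, CBC, CMP and ECG.
- **Dosing Adjustment/Schedule:** "The CBD cannot be stopped all at once as this could cause the patients seizures/epilepsy to become worse". For tapers, "these decreases will occur in 5 mg/kg/day increments every two week", or at another rate the treating provider finds appropriate.
- **Serious Adverse Events:** SAEs count "through 30 DAYS after administration of the last dose of study medication".

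**The concern.** The DSMB sentence names follow-up and precautions, rules them out, and allows one exception. Staff who applied it as written would close the study after the early termination visit. They would drop the post-wean visit and the active follow-up of ongoing AEs and raised liver tests.

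A child who withdraws alone keeps the post-termination visit. A child whose study is closed for safety would get less active follow-up, at the moment when unresolved AEs and raised liver tests are most likely. The protocol itself warns that seizures may worsen if CBD is stopped suddenly. The first primary safety measure in the Data Analysis section is a more than doubling of seizure frequency that leads to emergency care or admission.

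**Working it through.** The check is mainly a comparison of text. No power, sample size or event count enters.

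**Step 1. Rules side by side**

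| Standing rule | Exception for a study stop? | Against the DSMB sentence |
|---|---|---|
| Follow ongoing clinically significant AEs (Adverse Events) | None; study termination is itself the trigger | Direct conflict |
| Follow raised liver tests to baseline (Dosing; Withdrawal) | None; covers all trial subjects | Direct conflict |
| Post-termination visit (Schedule; visit text) | None | Direct conflict: not the visit named as the exception |
| No abrupt stop of CBD (Dosing) | None; unconditional | Indirect: precautions are excluded, but no abrupt stop is ordered |
| 30-day SAE window (Serious Adverse Events) | None | No scheduled contact left in the window |

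**Step 2. How far after the stop these rules reach**

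Inputs: taper step 5 mg/kg/day every 14 days (Dosing Adjustment/Schedule); standard maximum 25 and absolute maximum 50 mg/kg/day (same section); visit about 28 days after the wean (Schedule of Events); SAE window 30 days after the last dose. Assumptions: the early termination visit is close to the stop date, and the first decrease comes either on the day of the stop or 14 days later.

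Number of steps n = dose / 5. First day without drug = 14 × (n − 1) if the first decrease is on day 0, or 14 × n if it is on day 14.

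- From 25: n = 5, so 14 × 4 = day 56 (week 8) to 14 × 5 = day 70 (week 10).
- From 50: n = 10, so 14 × 9 = day 126 (week 18) to 14 × 10 = day 140 (week 20).
- Post-termination visit, adding 28 days: days 84 to 98 (weeks 12 to 14) from 25; days 154 to 168 (weeks 22 to 24) from 50.
- End of SAE window, adding 30 days: days 86 to 100 from 25; days 156 to 170 from 50.

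**Step 3. A faster wean**

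The provider may choose another rate. If the interval were halved to 7 days (an assumption, for illustration), the wean would end on days 28 to 35 from 25 and days 63 to 70 from 50. The visit would then fall on days 56 to 63 and days 91 to 98. The times shorten, but the visit is still well after the stop.

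**Step 4. The two descriptions of the visit**

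The Schedule of Events counts 28 days from the wean. The heading in the visit text counts from the end of the CBD study and does not say whether that means the child's own last treatment or the closing of the study. On the first meaning the two roughly agree; on the second they do not.

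**The case against.** The strongest reply is that the word special carries meaning: nothing beyond routine protocol procedures will be added, and the standing rules stay in force. On this view the early termination visit is named only because elsewhere it follows an individual decision, so the sentence has to extend it to everyone. This reading is possible but weak. The one exception named is itself a routine protocol visit, and naming it alone implies that the other routine visit, the post-termination one, is excluded.

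Several mitigating points stand. Families can reach study staff at all times, and clinically significant, related AEs after termination are still recorded, so passive reporting continues. The early termination visit is substantial, with CBC, CMP, urinalysis and ECG. The primary neurologist continues ordinary care. However, the protocol describes that care as unrelated to the CBD study, and CBD orders are filled only by the investigational pharmacy on the principal investigator's order. CBD-related follow-up would therefore be left with nobody named.

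A reader might infer more than the documents support:

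- **That children would be taken off CBD abruptly.** The sentence does not say so. The ban on abrupt stopping is unconditional, the wean decision belongs to the early termination visit, and the Schedule of Events allows dispensing there if needed. The default taper rate is also written for side effects or poor tolerability, not for a study stop.
- **That the post-termination visit would fall on day 28, in mid-wean.** This requires the visit-text heading to mean the stop date, which the protocol does not say.
- **That no visits during the wean is a consequence of this sentence.** None is specifically scheduled for a child who withdraws alone either.

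**Conclusion.** The contradiction is real for three rules: follow-up of ongoing clinically significant AEs, follow-up of raised liver tests, and the post-termination visit. For weaning, the fault is only that the sentence excludes precautions without repeating that the ban on abrupt stopping applies.

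At the default rate, the lost visit lies 12 to 14 weeks after the stop from 25 mg/kg/day and 22 to 24 weeks after it from 50; a faster wean shortens this. These figures rest on the two assumed dates for the first decrease.

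The point should be corrected because the sentence would be used when safety follow-up matters most. It concerns participant safety only. The SAP reports a completed analysis of the first 12 months in 89 enrolled children, and nothing here changes that analysis. Neither document says the study was stopped.

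**What to change.** Replace the DSMB sentence with text to this effect:

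> If the study is stopped, every child on CBD has the early termination visit. CBD is weaned and not stopped all at once (see Dosing Adjustment/Schedule). Wean drug is dispensed at that visit if needed, subject to availability from the supplier. The post-termination visit, the 30-day SAE window, and follow-up of ongoing clinically significant AEs and elevated LFTs apply as already specified. No further special procedures will occur.

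Change the heading of the post-termination visit text so that, like the Schedule of Events, it counts from the CBD wean.

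Do not promise drug supply outright. CBD comes from one company, and that company or a regulator can end participation, so the investigator may not control it. The 25% stopping rule needs no change for this point.

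The cost is one replaced passage and one heading. If the study stops, it adds one already-defined visit per child on drug; otherwise nothing.
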